Data collection. The program manager (PM) will track recruitment and retention. A clinical assessor will conduct diagnostic interviews and questionnaire evaluations pre-, mid-, and post-intervention blind to group allocation. All pre-, mid-, and post-treatment biological measures will be conducted and analyzed by the psychophysiological and consultants, blind to group allocation.

Assessment, Data Collection, and Schedule. Instruments and other data collection tools and their description are in the [Assessment Detail](#). This strategy includes repeat measures yet minimizes response burden. Our goal is to test for effect signal. It is premature to evaluate durability and not ethical to keep subjects in a protocol where they may not be receiving effective treatment (particularly true of MIN), so we will not include a six-month follow-up period. Instead, a one-month follow-up will test symptoms and functioning and be utilized to re-connect participants to clinical services. Data collection at mid-point of treatment is warranted to replicate mid-treatment findings from our first trial. Such a finding may help determine dose effects and plan a dose-finding trial.

Outcome measures. The primary outcome is change in PTSD symptom severity from pre- to post-treatment. We hypothesize a large pre- to post-treatment effect for ACU ($d \geq 0.8$) and at least a mild treatment effect ($d \geq 0.30$) of the difference between groups (ACU vs MIN) pre- to post-treatment, with 80% probability of detecting a true group difference at $p < 0.05$ (2-sided). Main biological outcome (secondary outcome) is change from pre- to post-treatment in PPR (decreased startle by EMG eyeblink).

IV. Statistical Plan and Data Analyses

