Startle. Startle will be measured by administering a 250 ms airblast with an intensity of 140 p.s.i. directed to the larynx as described in similar human fear conditioning studies (Norrholm et al, 2011), recording the participants' electromyographic (EMG) activity during eyeblink muscle contractions. EMG startle eyeblink responses will be recorded using two 5mm Ag/AgCl electrodes placed over the orbicularis oculi muscle of the left eye. One electrode will be placed directly below the pupil in forward gaze while the other will be placed about 1 cm lateral to the first. Both electrodes will be placed as close to the eye as possible while still allowing the participant to close his or her eyes comfortably. Impedance between the two electrodes will be measured and deemed acceptable if below 10 k Ω . Startle responses will be rectified and integrated for analysis using a 20 ms time constant. In order to be scored, the onset of the blink response must occur within a window of 20 to 100 ms after startle probe onset. The blink response must reach peak amplitude within a window of 20 to 150 ms following the startle probe. Amplitudes will be recorded as the difference between the peak activity value and the baseline level that was present immediately preceding onset of the blink response. Participants who fail to reach 1 μ V amplitudes on more than 50% of probed trials will be considered non-responders and will be excluded from further EMG analyses.

Heart rate. Electrocardiogram (ECG) activity will be recorded throughout the experiment by employing a Lead 1 electrode placement. Electrode sites will be cleaned with alcohol prep pads to improve contact.

Skin Conductance. EDA will be recorded by Ag/AgCl electrodes (Unibase gel) attached to the distal phalanx of index and middle fingers to measure skin conductance level (SCL) and skin conductance response (SCR).

General measurement procedure. All PPR measures (secondary and exploratory outcomes) will be obtained in a single visit at each timepoint. There are two procedures at each visit, and these total 49 minutes of recording time. We expect the total visit with set-up, prep, and wrap-up to take approximately 70 minutes. This includes a 15-minute rest period at the beginning to help diminish anticipatory anxiety.

Procedure	Baseline	Fear Conditioning
	5 minutes	44 minutes
Assessed Variable(s)	SC, HRV	Startle, HR, SCR

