The fear conditioning paradigm will consist of 2 experimental sessions at each testing timepoint. Testing will occur at baseline, during mid-treatment, post-treatment, and at 6-month follow-up. The fear conditioning sessions, described below, include an Acquisition session based on the AX+/BX- design and an Extinction session:

Acquisition (AX+/BX-) Session. Methodology will be similar to those employed in past studies (Jovanovic et al, 2009). The session will begin with a Habituation Phase consisting of six acoustic startle probes presented alone, referred to as noise alone (NA) trials, to reduce initial startle reactivity. This will be followed by a Pre-exposure Phase, during which the participants will view the shapes (A, B, and X) but they will not be paired with the US. The Acquisition Phase will include 3 blocks with 12 trials (4 AX+, 4 BX-, and 4 NA trials) in each block for a total of 36 trials. The Inhibition Testing Phase will consist of a block of 3 NA trials and 3 trials with A and B presented together. In the AX+ trials, two shapes of different color will be presented together with a "+" between them to encourage elemental processing of the shapes. The shapes will be presented for 6 seconds. The startle probe (40 ms burst of white noise at 106 dB) will occur 6 seconds after shape onset; the shape presentation will co-terminate with the US 500 ms later. BX and AB trials will also contain two different colored shapes, and a startle probe presented 6 seconds after shape onset, but there will be no US in these trials. A Re-conditioning block of 12 trials (4 AX+, 4 BX-, and 4 NA) will be presented at the end of the session to increase the fear response prior to extinction. Inter-trial intervals will be randomized between 9 and 22 seconds.

Extinction Session. After a ten-minute rest period following the completion of the Acquisition session or AX+/BX-, the same shapes will once again be presented in semi-random order. The extinction phase will include 4 blocks of 12 trials (4 AX, 4 BX, and 4 NA) in each block for a total of 48 trials. During Extinction, the AX trials will no longer be paired with the presentation of the US. The US will not be presented at any time during the Extinction phase. Startle probes will still be delivered for 40 ms during shape presentation, 6 seconds after shape onset, and will co-terminate with each stimulus. Inter-trial intervals will again be randomized between 9 and 22 seconds.

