Acupuncture for PTSD in Combat Veterans
A VA Merit Review Study
Principal Investigator: [name].

Data Analysis Plan

General Approach. General linear mixed models (GLMM) is capable of handling multiple underlying distribution and model structures through link functions, such as repeated measures random effects models of continuous outcomes (identity link), repeated measures logistic models (logit link), and Poisson and negative binomial models (log link). In addition to modeling global fixed effects across subjects, GLMM can also model individual subject random effects. Survival analysis allows for the assessment of time to event modeling using probability estimates on survivor functions and estimates of hazard ratios. Time to event modeling using Cox proportional hazard modeling allows for all subjects to contribute information to the model up until occurrence of event, drop out, or end of study. Cox Proportional Hazards modeling will be used to investigate for effect-size of the treatment by allowing subjects to contribute their information to the model while they are being observed and censored once they are no longer being observed (loss to follow-up or end of study period). Further, using the Cox modeling we will investigate for time dependencies and informative loss to follow-up. In the case where dropouts may be associated with the treatment assignments, we will leverage intention to treat methodology and construct a piecewise random effects model with both "on-" and "off-treatment" slopes. GLMM will be used to evaluate the primary clinical hypothesized effects of treatment (ACU) on the clinical outcome of PTSD symptom severity (CAPS) over time (mid- and end-treatment, and 1-month follow-up), controlling for baseline severity of symptoms and demographic characteristics (e.g., age, gender) in comparison with placebo control group (MIN) with assumption of intent to treat. Cohen's *d* within and between subjects will be calculated. Interaction terms will be included in the models to evaluate treatment fidelity and treatment expectancy as potential moderators.

GLMM will also be used to evaluate the secondary biological hypothesized effects of treatment on pre- to post-treatment in PPR (decreased EMG eyeblink). These same statistical procedures (GLMM, survival analysis, and Cohen's *d* with intent to treat) will be applied to evaluate exploratory outcomes: clinical symptoms comorbid with PTSD, PPR (HR, HRV, SCR), and PTSD diagnosis.

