This was determined using a formula for a random effects modeling (Montgomery, 1991), which may determine the necessary sample size to detect a statistically significant difference in treatment/control group means at different levels of projected effect differences.

$$n = \frac{2 * a * M^2 * \Phi^{*2}}{\Delta^2}$$

Where:

M = measure of noncentrality parameter to estimate the standard normal probability of making a type II error

n = number of replicates necessary for each treatment

a = number of treatments (a=2)

Φ^* = estimated standard deviation

Δ = difference in baseline and post treatment

Table. Examples of sample sizes necessary for significance testing at different mean and SD’s (between group: treatment (ACU) and control (MIN)) for PTSD severity (primary outcome) at power = 0.80.

Mean difference between ACU and MIN PTSD severity scores post-treatment	Φ^2	Total N Using Formula Above
8.5	12	62
	14.4	90
	15	96
	20	162
12	12	32
	15	50
	20	86

Recruitment goals are N=90, 45 per group. With a post-randomization attrition rate of 10% we will have at least 40 individuals in each group. Considering attrition, the above table indicates that for an average difference in means of 12 at end-treatment with a standard deviation of 15, a total sample size of 50 (25 in each group) would

be more than adequate to report a statistical difference with 80% power. If differences in treatment group means were found to be larger than 12, we would need even fewer subjects in our treatment groups to achieve statistical significance.

PPR Data Recording and Reduction. A description of the procedure/data is in [Appendix 4](#). Data reduction and analyses will follow current established protocols in our lab (Norrholm et al, 2011a). Data will be collected with the BioSemi recording software (BioSemi B.V, Amsterdam, Netherlands) and the resulting data will be exported to Mindware software (Mindware Technologies LTD, Gahanna, OH) for data reduction and generation of analyzable variables.

Startle data reduction for analyses. The raw EMG signal will be recorded at a rate of 1000 Hz throughout the experimental session using a 28 Hz high pass and 500 Hz low pass filter (as recommended by guidelines for human eyeblink startle in Blumenthal et al., 2005; *Psychophysiology*, 42:1-15). Raw signals will be stored and exported for analysis in microvolt (μV) values.

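### Does the startle non-responder rule drop patients because of how they responded to treatment?

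*Protocol*

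**What the plan says.** The rule is in the Protocol, Assessment Detail, item 3, under Startle. Participants whose blink does not reach 1 µV "on more than 50% of probed trials will be considered non-responders and will be excluded from further EMG analyses". No visit is named, and nothing says whether trials are judged per visit or pooled.

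The SAP does not repeat the rule. Its section on PPR data recording and reduction points to an Appendix 4 and adds: "Data reduction and analyses will follow current established protocols in our lab". The protocol has the same text. Neither the appendix nor the laboratory protocols are in the supplied documents.

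On timing, the fear conditioning section of the protocol states: "Testing will occur at baseline, during mid-treatment, post-treatment, and at 6-month follow-up". The outline of steps puts the pre-treatment evaluation before randomisation.

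On the endpoint, the protocol's outcome measures paragraph reads: "Main biological outcome (secondary outcome) is change from pre- to post-treatment in PPR (decreased startle by EMG eyeblink". The SAP's General Approach refers to "the secondary biological hypothesized effects of treatment on pre- to post-treatment in PPR (decreased EMG eyeblink". Neither says whether this means overall blink amplitude or fear-potentiated startle, the relative increase that the Background describes. Neither fixes an analysis scale.

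On the stimulus, the Startle paragraph opens with "Startle will be measured by administering a 250 ms airblast", while the Acquisition Session says "The startle probe (40 ms burst of white noise at 106 dB) will occur 6 seconds after shape onset".

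**The concern.** The rule is judged on blink amplitude, and benefit is defined as a lower blink amplitude. If the check were repeated after treatment, a patient whose blink fell below 1 µV because acupuncture worked would be labelled a non-responder and removed. More ACU than MIN patients would go, and the comparison would no longer describe everyone who gave a scorable blink at baseline. That is selection on the outcome after randomisation, in a plan that says its analyses are by intent to treat. Startle is the only named secondary outcome.

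The two descriptions of the startle stimulus add doubt about which trials form the denominator of the 50% rule.

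**Working it through.** **The plan's own figures.** No startle amplitude, SD, non-responder rate or power is given, so there is no startle figure to reproduce. The only sizing is for CAPS-5: 2 × (1.960 + 0.842)² × 14.4² / 8.5² = 45.05 per arm, in line with the stated 90. It is used here only to turn percentages into head counts out of 45.

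**Which trials count.** From the session descriptions, and assuming that the pre-exposure phase carries no probe, the noise probes per visit are:
- habituation 6, acquisition 36, inhibition test 6, re-conditioning 12, extinction 48; total 108;
- by type: 41 noise-alone, 32 BX, 32 AX, 3 AB.

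Exclusion needs more than 54 failures. The fear-potentiated trials (AX and AB) are 35 of 108, or 32%, so losing the blink on all of them does not by itself trigger the rule. Airblasts occur on only 12 + 4 = 16 trials, all AX+. For extinction the protocol says: "The US will not be presented at any time during the Extinction phase".

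**What each reading does.** Amplitudes are assumed log-normal with median m and between-patient log SD s. The trial log SD is 0.6, the correlation between visits 0.7, and ACU lowers every probe by a fraction r. There were 400,000 simulated patients per arm and setting. With many trials per visit, failing is close to having a personal median below 1 µV, so P(fail) ≈ Φ(−ln m / s). For m = 3 and s = 0.8 this is Φ(−1.373) = 0.085; the simulation gives 0.084.

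- *Judged once at baseline:* exclusions are equal by arm (8.4% and 8.4% at m = 3, s = 0.8), and there is no bias for any r.
- *Judged at each visit, r = 0:* 2.1 against 2.1 of 45 are newly excluded (m = 3, s = 0.8), and there is no bias.
- *Judged at each visit, r = 30%, s = 0.8:*

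| Median (µV) | Newly excluded of 45, ACU / MIN | Log effect, baseline rule → per-visit rule | Unadjusted µV change, baseline rule → per-visit rule |
|---|---|---|---|
| 2 | 8.4 / 3.8 | −0.355 → −0.288 (19% smaller) | −1.14 → −1.21 (6% larger) |
| 3 | 5.4 / 2.1 | −0.354 → −0.312 (12% smaller) | −1.56 → −1.64 (5% larger) |
| 5 | 2.1 / 0.7 | −0.357 → −0.338 (5% smaller) | −2.53 → −2.59 (2% larger) |
| 10 | 0.3 / 0.1 | −0.359 → −0.355 (1% smaller) | −4.98 → −5.00 (0.4% larger) |

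The largest log-scale shrinkage in the grid is 23% (median 2, s = 1.0, r = 50%; 12.9 against 4.5 newly excluded). The same s and r at median 10 give 4%. A second set of runs, with correlation 0.6 and s up to 1.2, gives 0–3% at median 20. On baseline-adjusted microvolts the shrinkage there is about 2–5% at median 3 and under 1% at medians 10–20.

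**Fear-potentiated endpoint.** If ACU removes only the AX/AB potentiation (assumed 0.3 log units), exclusions among baseline responders differ between arms by at most 1.5 percentage points on the 108 noise probes.

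**The case for a change.** The strongest case for a change is that the text really is silent. The rule sits in a measurement section that applies to every visit, and an analyst could run it on each recording. The endpoint phrases in both documents speak of a decreased eyeblink, which leaves overall amplitude open. If amplitudes are low, the loss is not trivial: at a median of 3 µV with a 50% reduction and s = 0.8, 10.5 ACU against 2.1 MIN patients of 45 would be newly excluded. Naming the baseline visit would take one sentence.

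The silence, the arithmetic and the low cost all stand. What does not stand is that following the plan gives a wrong result. The sentence labels participants and removes them from all further EMG work, which is a one-time status. A baseline check is unbiased, and pooling trials over visits leaves a log-scale bias within about 1.5%. Only the per-visit reading does harm, and neither document states it. The unsupplied appendix or laboratory protocol may already settle the visit.

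Two supporting arguments are weaker than they look. The sentence in the Recruitment section about retaining data concerns subjects who withdraw, not unscorable recordings; only the general intent-to-treat statements bear on this. The airblast sentence is loose drafting. The same paragraph times the blink from the startle probe, the fear conditioning section defines the airblast as the unconditioned stimulus, and the Acquisition Session defines the probe as the noise burst. Taking the airblast as the probe would leave no scored trials in extinction, which the study is built to measure.

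**Conclusion.** The concern does not call for a change. The plan leaves out a detail that an analyst would fill sensibly: judge non-responder status once, on the session before randomisation, and keep later low but technically valid amplitudes as data. The airblast wording is a clerical slip that the session descriptions resolve.

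The per-visit reading would matter only with an overall-amplitude endpoint, a true ACU effect on all probes, and amplitudes near 1 µV. Its size then rests wholly on assumed values. In the main grid, log-scale shrinkage runs from about 1% at a median of 10 µV to 23% at 2 µV. The direction reverses on unadjusted microvolt change, and microvolts are the only unit the documents name. There is no bias under the null, none with a baseline rule, and no effect on the CAPS-5 primary analysis. Confidence is moderate, because the appendix and laboratory protocols could not be checked.

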Acupuncture for PTSD in Combat Veterans
A VA Merit Review Study
Principal Investigator: [name].

Data Analysis Plan

General Approach. General linear mixed models (GLMM) is capable of handling multiple underlying distribution and model structures through link functions, such as repeated measures random effects models of continuous outcomes (identity link), repeated measures logistic models (logit link), and Poisson and negative binomial models (log link). In addition to modeling global fixed effects across subjects, GLMM can also model individual subject random effects. Survival analysis allows for the assessment of time to event modeling using probability estimates on survivor functions and estimates of hazard ratios. Time to event modeling using Cox proportional hazard modeling allows for all subjects to contribute information to the model up until occurrence of event, drop out, or end of study. Cox Proportional Hazards modeling will be used to investigate for effect-size of the treatment by allowing subjects to contribute their information to the model while they are being observed and censored once they are no longer being observed (loss to follow-up or end of study period). Further, using the Cox modeling we will investigate for time dependencies and informative loss to follow-up. In the case where dropouts may be associated with the treatment assignments, we will leverage intention to treat methodology and construct a piecewise random effects model with both "on-" and "off-treatment" slopes. GLMM will be used to evaluate the primary clinical hypothesized effects of treatment (ACU) on the clinical outcome of PTSD symptom severity (CAPS) over time (mid- and end-treatment, and 1-month follow-up), controlling for baseline severity of symptoms and demographic characteristics (e.g., age, gender) in comparison with placebo control group (MIN) with assumption of intent to treat. Cohen's *d* within and between subjects will be calculated. Interaction terms will be included in the models to evaluate treatment fidelity and treatment expectancy as potential moderators.

GLMM will also be used to evaluate the secondary biological hypothesized effects of treatment on pre- to post-treatment in PPR (decreased EMG eyeblink). These same statistical procedures (GLMM, survival analysis, and Cohen's *d* with intent to treat) will be applied to evaluate exploratory outcomes: clinical symptoms comorbid with PTSD, PPR (HR, HRV, SCR), and PTSD diagnosis.

Statistical Analyses, Primary Hypothesis. Prior to the application of any statistical modeling, underlying assumptions and conditions will be examined. Univariate analyses, including tests of distribution assumptions, t-tests, and chi-square tests will be conducted to determine possible significant covariates to be included in further multivariable modeling as well as to investigate efficiency of randomization techniques. All models will be assessed for goodness of fit as well as other diagnostics including assessment for collinearity performed on all covariates chosen for subsequent analyses. Repeated measures analysis of variance will be used to formally test the null hypothesis of no differences in baseline PTSD symptom mean levels and subsequent retest of PTSD symptom mean levels while simultaneously adjusting for any significant covariates. All models will be run accounting for any potential confounders. Analyses will be performed assuming intent to treat and informative loss-to-follow up will be investigated. Additional analyses will be conducted to determine interactions and mediating effects while simultaneously adjusting for other covariates in the model.

Assumptions for Power Calculations. Assumptions are based on interpolated data since primary outcomes in our first ACU study were assessed with the PSS-SR scale and there are no PTSD studies using MIN as the sham. Furthermore, to be consistent with major PTSD research, we will use the CAPS-5 (DSM-5 version) as the primary outcome, and there are as of yet no completed clinical trials using CAPS-5. In our first study, mean pre-treatment PTSD severity score was about 62% of maximum (31.55 of 51). ACU mean decreased 50% - 31.33 (10.1) to 15.65 (13.95) and wait-list mean decreased 9.3% - 30.79 (9.54) to 27.92 (12.33) at post-treatment. We thus assume that subjects will have a baseline mean CAPS-5 score of 50 (10) and a 50% reduction of symptoms and a 38% increased variance (CAPS-5 = 25; SD = 13.8) with ACU. There are sparse data about effects of

MIN, noting a 33% improvement compared to pharmacological treatment only, and a 33% less effect than ACU in the Shen study. A 2010 Cochrane systematic review of over 200 trials investigating 60 clinical conditions about general placebo effect found placebos to not have important clinical effects but may influence patient-reported outcomes in some situations (e.g. pain and nausea). The pooled relative risk calculated for placebo was 0.93 (effect of only 7%) but significant. Confidence intervals are generally wide in the placebo arm. Several clinical and methodological factors were associated with higher effects of placebo. Since our study includes some of these factors, and since we expect MIN to have some physical effect, MIN could provide an effect as much as 33% with a wider variance. This would predict mean CAPS-5 scores (MIN) at end-treatment of 33.5 (SD 15). The conservative prediction is mean CAPS-5 reductions of 25 points with ACU and 16.5 points with MIN, an 8.5 point difference with a pooled SD of 14.4. Given our experience and data about placebo effect, we can modestly expect a 12 point between group CAPS-5 difference and a pooled SD of 15.

Treatment Effects, Power and Sample Size, Primary Hypothesis. “The efficacy of verum acupuncture (ACU) for PTSD symptom severity will be large (pre- to post-treatment Cohen’s $d \geq 0.8$), and significantly better than sham acupuncture (MIN) (between group Cohen’s $d \geq 0.30$, with 80% probability of detecting a true group difference at $p < 0.05$ (2-sided).”

Effects. The conservative assumptions noted above will result in pre- to post-treatment Cohen’s $d = 2.07$ within group (ACU) and between group (post-treatment difference) Cohen’s $d = 0.59$, which will prove the null hypothesis false and show a large treatment effect for ACU and a moderate between-group effect size.

Sample size needed and power. The conservative assumptions would require a total of 90 patients in a two-treatment parallel-design to provide a probability of 80 percent to detect a treatment difference at a two-sided 0.05 significance level. Modest assumptions of a 12 point difference with a pooled SD of 15 requires a total of 50 patients with power of 0.80 at alpha < 0.05 .

This was determined using a formula for a random effects modeling (Montgomery, 1991), which may determine the necessary sample size to detect a statistically significant difference in treatment/control group means at different levels of projected effect differences.

$$n = \frac{2 * a * M^2 * \Phi^{*2}}{\Delta^2}$$

Where:

M = measure of noncentrality parameter to estimate the standard normal probability of making a type II error

n = number of replicates necessary for each treatment

a = number of treatments (a=2)

Φ^* = estimated standard deviation

Δ = difference in baseline and post treatment

Table. Examples of sample sizes necessary for significance testing at different mean and SD’s (between group: treatment (ACU) and control (MIN)) for PTSD severity (primary outcome) at power = 0.80.

Mean difference between ACU and MIN PTSD severity scores post-treatment	Φ^2	Total N Using Formula Above
8.5	12	62
	14.4	90
	15	96
	20	162
12	12	32
	15	50
	20	86

Recruitment goals are N=90, 45 per group. With a post-randomization attrition rate of 10% we will have at least 40 individuals in each group. Considering attrition, the above table indicates that for an average difference in means of 12 at end-treatment with a standard deviation of 15, a total sample size of 50 (25 in each group) would

be more than adequate to report a statistical difference with 80% power. If differences in treatment group means were found to be larger than 12, we would need even fewer subjects in our treatment groups to achieve statistical significance.

PPR Data Recording and Reduction. A description of the procedure/data is in [Appendix 4](#). Data reduction and analyses will follow current established protocols in our lab (Norrholm et al, 2011a). Data will be collected with the BioSemi recording software (BioSemi B.V, Amsterdam, Netherlands) and the resulting data will be exported to Mindware software (Mindware Technologies LTD, Gahanna, OH) for data reduction and generation of analyzable variables.

Startle data reduction for analyses. The raw EMG signal will be recorded at a rate of 1000 Hz throughout the experimental session using a 28 Hz high pass and 500 Hz low pass filter (as recommended by guidelines for human eyeblink startle in Blumenthal et al., 2005; *Psychophysiology*, 42:1-15). Raw signals will be stored and exported for analysis in microvolt (μV) values.

Skin Conductance Response. Skin conductance responses are scored as the largest amplitude responses beginning in a window of 1 to 3 seconds following stimulus onset. A response is defined as having amplitude greater than $0.01 \mu\text{S}$ relative to the pre-stimulus baseline (Boucsein et al, 2012).

Heart rate. Average heart rate (HR), the standard deviation of the HR, power of high frequency (HF), low frequency (LF), very low frequency (VLF) components, % power of LF (%LF [of VLF+LF+HF]) and of HF (%) and the ratio of the LF over the HF (LF/HF ratio is used as an indirect autonomic balance index) of HRV are calculated as cardiac activity measures. Artifact-corrected 3-min long recording epochs are analyzed with FFT to assess HRV. Inter-beat Intervals (IBIs) will be scored as the time difference between successive R waves in the ECG signal. IBIs will be used as the dependent variable analyzed instead of heart rate because of a lowered susceptibility to artifact due to differences in baseline values (Stern et al., 2001). A window of 3 seconds pre-stimulus onset to 6 following stimulus onset will be scored. Instantaneous IBIs will be recorded at half-second intervals during the pre- and post-stimulus time windows. A difference score between the average pre-stimulus IBI for each trial and each post-stimulus IBI value will be computed for each trial. IBIs will later be converted heart rate (beats per minute) for more readily interpretable post-analytic write-ups.

Respiration. Respiration will be scored in a similar fashion to the ECG data, and reported in interbreath intervals. Peak detection of each positive deflecting curve in the breathing cycle will be manually reviewed visually in order to assess accuracy. Interbreath intervals will later be converted to respiration rate (breaths per minute) for ease of interpretation.
